5.1 Inclusion Criteria

Subjects who meet all the following inclusion criteria can be enrolled into the study:

Inclusion Criteria	Rationale	Screening	Admission (Day -3)
1. Subject has signed the ICF and is able to understand the information provided in the ICF.	Administrative	X	
2. Subject is aged \geq 28 years.	Safety	X	
3. Subject is of Caucasian origin.	Effect	X	
4. Currently smoking, healthy subject as judged by the Investigator or designee based on assessments from the Screening Period (e.g., safety laboratory, spirometry, vital signs, physical examination, ECG, medical history, and X-ray).	Safety	X	X
5. Subject smokes at least 10 commercially available non-menthol CCs per day (no brand restrictions) with a maximum yield of 1 mg nicotine ISO/CC, as labelled on the cigarette package, at least for the last 6 weeks prior to the Screening Visit and Admission, respectively, based on self-reporting. The smoking status will be verified based on a urinary cotinine test (cotinine \geq 200 ng/mL).	Effect	X	X
6. The subject has been smoking at least for the last 10 years.	Effect	X	X

Confidentiality Statement

Data and information contained in this document are considered to constitute trade secrets and confidential commercial information, and the legal protections provided to such trade secrets and confidential information are hereby claimed under the provisions of applicable law. No part of this document may be publicly disclosed without the written consent of Philip Morris Products S.A.

Inclusion Criteria	Rationale	Screening	Admission (Day -3)
7. The subject does not plan to quit smoking in the next 6 months as assessed by Prochaska "Stage of Change" Questionnaire.	Safety	X	
8. The subject is ready to comply with the study protocol (e.g., to use CHTP 1.2).	Effect	X	X

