6.7.1.2 Ambulatory Period

Subjects in the CHTP 1.2 arm will be instructed to exclusively use CHTP 1.2.

On the first day of Visit 2, Visit 3, and Visit 4, subjects in the CHTP 1.2 and CC arms will be allowed to use their assigned product from the time of check-in until around 11:00 PM. On the

Confidentiality Statement

Data and information contained in this document are considered to constitute trade secrets and confidential commercial information, and the legal protections provided to such trade secrets and confidential information are hereby claimed under the provisions of applicable law. No part of this document may be publicly disclosed without the written consent of Philip Morris Products S.A.

second day of Visit 2 and Visit 3 product use will be allowed from 06:30 AM onwards. The exposure period to the assigned IP will end at 11:00 PM on the first day of Visit 4. On the second day of Visit 4 (Day 91), subjects who wish to smoke CC or use other nicotine/tobacco-containing products will be allowed to do so, but only after the end of 24-hour urine collection and after spirometry and sampling for CYP2A6 activity have been performed.

During the ambulatory visits (Visit 2, Visit 3, Visit 4) the use of CHTP 1.2 will be strictly forbidden for subjects in the CC arm.

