7.7.2.1 Fagerström Test for Nicotine Dependence (Revised Version)

Potential nicotine dependence will be assessed via a subject self-reported questionnaire using the Fagerström Test for Nicotine Dependence (FTND) in its revised version [40].

The questionnaire consists of six questions which will be answered by the subject himself/herself. The scores obtained on the test allow the classification of nicotine dependence in three different levels: mild (0-3 points), moderate (4-6 points), and severe (7-10 points) with regards to CC at the Screening Visit and the assigned product at Visit 4. .

See [Appendix A](#) for the time points of assessment.

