5.3 Exploratory Objectives and Endpoints

1. To describe the following parameters in smokers switching from CC to CHTP 1.2 as compared to smokers continuing to use CC
- Excretion of mutagenic material in 24-hour urine

Endpoints:

- Ames mutagenicity test (YG1024+S9): Day 5 and Day 90 Visit.
- Subjective effects of smoking

Endpoints:

- Questionnaire of Smoking Urges (QSU), (brief version): Day 1 to Day 90 Visit.
- Fagerström Test for Nicotine Dependence (FTND), (revised version): Day 90 Visit.
- Product evaluation: Modified Cigarette Evaluation Questionnaire (MCEQ): Day 1 to Day 90 Visit.
- Cytochrome P450 2A6 (CYP2A6) enzymatic activity

Endpoints:

- the molar metabolic ratio of trans-3'-hydroxycotinine/cotinine: Day 6 and Day 90 Visit.
- Intent to Use of CHTP 1.2

Endpoints:

- Intent to Use of CHTP 1.2 Questionnaire (ITUQ): only in smokers switching from CC to CHTP 1.2: Day 6 and Day 90 Visit

2. To describe the CHTP 1.2 use over the entire exposure period according to the product preference of the subject

Endpoint (daily):

- Number of CC or CHTP 1.2 used daily as reported on the usage log during the confinement period and self-reported number of any nicotine/tobacco product use on a daily basis as reported on the product use diary during the ambulatory period according to product preference

3. To assess the smokers' mental state for the intention to quit

Endpoint (Day 90 Visit):

- Prochaska "Stage of Change" Questionnaire

4. To monitor BoExp and clinical risk endpoints in subjects who attempt to quit using tobacco products according to the time since they quit ^a

Endpoints:

- BoExp: MHBMA, S-PMA, 3-HPMA, COHb, and total NNAL
- CO (expressed as ppm) in exhaled breath
- Selected clinical risk endpoints (hs-CRP, homocysteine, blood glucose, LDL, HDL, TG, TC, fibrinogen, HbA1c, sICAM-1, WBC, platelet count, Apo A1, Apo B, 11-DTX-B2, and clinical risk endpoints related to oxidative stress) in respective body matrix

^a The reporting of the objective will be the subject of an appendix to the main clinical study report.

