7.4.6 Prochaska “State of Change” Questionnaire: Intention to Quit Smoking

The Prochaska’s “Stage of Change” Questionnaire will be used to assess the smokers’ mental state for the intention to quit (DiClemente et al, 1991; Velicer et al, 1995). There are 5 stages of change describing smokers and former smokers: 1. Precontemplation, 2. Contemplation. 3. Preparation. 4. Action. 5. Maintenance.

- In the “Precontemplation” stage, the individual does not recognize smoking as a problem
- In the “Contemplation” stage, the individual is gathering information about smoking, such as contacting a health care provider or a tobacco quit line for information on the effects of smoking or smoking cessation consequences. During this stage, the stress and inconvenience of quitting smoking is greater than the immediate and possible long-term health effects of continuing smoking
- In the “Preparation” stage, intention and behavior begin to come together and the subject is preparing to enter into action in the next 30 days. It is necessary for the subject to recognize the benefits of not smoking, before a subject can enter the “Action” stage and as a result, changes his/her smoking behavior
- After six months of not smoking, the individual reaches the “Maintenance” stage when different skills may be needed to prevent relapse from smoking
- The structure of the questionnaire is shown in Figure 3 and the scoring algorithm is shown in Table 5.

Figure 3: Structure of Prochaska's "Stage of Change" Questionnaire

[figure not shown]

Table 5: Scoring algorithm

Assessment:

1. Are you currently a smoker?
 - A) Yes, I currently smoke
 - B) No, I quit within the last 6 months
 - C) No, I quit more than 6 months ago
 - D) No, I have never smoked

Smokers only:

2. In the last year, how many times have you quit smoking for at least 24 hours? ____
3. Are you seriously thinking of quitting smoking?
 - A) Yes, within the next 30 days
 - B) Yes, within the next 6 months
 - C) No, not thinking of quitting

Scoring Sheet (do not read to subject):

1. Are you currently a smoker?
 - A) Yes, I currently smoke
 - B) No, I quit within the last 6 months (ACTION STAGE)
 - C) No, I quit more than 6 months ago (MAINTENANCE STAGE)
 - D) No, I have never smoked (NONSMOKER)

Smokers only:

2. In the last year, how many times have you quit smoking for at least 24 hours? -----
3. Are you seriously thinking of quitting smoking?

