10.7 Quitters Population

The quitters population consists of all subjects from the Full Analysis Set who had no CC, CHTP, e-cigarette or other tobacco products for at least 14 days prior to Discharge at Day 90 Visit or the date of early termination as reported in the product use diary.

If there are at least 10 subjects in any treatment group and timepoint who attempted to quit (see **Table 7**), the table with descriptive statistics will be repeated for that group. These tables will then get an additional “.1” to the table numbering and “by attempt to quit” will be added in the title. Subjects who restart any tobacco product use will not be included in this analysis. Otherwise, these data will be included in the listings only.

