12.5.3.1.5 Prochaska “State of Change” Questionnaire: Intention to Quit Smoking

The stages of change will be cross-tabulated (screening vs Day 90 Visit) per arm (Table 15.2.5.8) and listed (Listing 15.3.5.5). The cross-tabulation will also be created per product use category (Table 15.2.5.8.1).

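### The Prochaska item on current smoking does not say whether CHTP 1.2 use counts, so 'Action' at Day 90 in the CHTP 1.2 arm may mix assigned product switching with quitting tobacco

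*SAP*

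**What the plan says.** Exploratory objective 3 (SAP 5.3; Protocol 3.3) is "To assess the smokers' mental state for the intention to quit", measured at the Day 90 Visit with the Prochaska questionnaire.

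The scoring is in SAP 7.4.6, Table 5, and is the same in Protocol Appendix C. Item 1 asks "1. Are you currently a smoker" and names no product. One of its answers is scored directly: "B) No, I quit within the last 6 months (ACTION STAGE"). Item 2 (24-hour quits in the last year) and item 3 (serious thoughts of quitting) are for smokers only.

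SAP 12.5.3.1.5 gives the output: "The stages of change will be cross-tabulated (screening vs Day 90 Visit) per arm" (Table 15.2.5.8), repeated by product use category (Table 15.2.5.8.1). Both tables are on the FAS and no test is planned.

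Four other provisions bear on how item 1 is answered and read:

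- Protocol 6.7.1.2: "Subjects in the CHTP 1.2 arm will be instructed to exclusively use CHTP 1.2".
- SAP 10.7 defines quitters as FAS subjects "who had no CC, CHTP, e-cigarette or other tobacco products for at least 14 days", according to the diary. CHTP use therefore disqualifies.
- Protocol 7.7.2.1 fixes the reference product of the FTND: "with regards to CC at the Screening Visit and the assigned product at Visit 4". There is no such sentence for the Prochaska.
- Protocol 5.1, criterion 7: "The subject does not plan to quit smoking in the next 6 months as assessed by Prochaska". Screening stage is therefore essentially Precontemplation for everyone.

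**The concern.** By Visit 4 a compliant CHTP 1.2 subject has gone about 90 days without cigarettes. Asked about smoking with no product named, that subject may say that he or she still smokes, or that he or she stopped within the last six months. Nothing in the available text chooses between the two. The second answer gives the Action stage, and the intention item is then skipped. The same person would not be a quitter under SAP 10.7.

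A CC-arm subject cannot reach Action through the assigned product. An ambiguous question thus becomes one that can act differently by arm, in a table laid out by arm. An unqualified rise in Action under CHTP 1.2 would be read as movement towards quitting, and the error would favour the test product.

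**Working it through.** The plan gives no figure to reproduce here. The check sets the passages side by side and then shows the possible range.

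**Reasoning through the text**

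1. Can a switcher truthfully give the Action answer? Protocol 6.3.3 requires exclusive CHTP 1.2 use from Day 1 in confinement, and Protocol 6.7.1.2 instructs it afterwards. About 90 days without cigarettes is inside six months, so a subject who takes the item to mean cigarettes picks the six-month answer.
2. Is intention then recorded? No. Items 2 and 3 are restricted to those who say they smoke.
3. Does the study treat such a subject as having quit? No. SAP 10.7 counts CHTP as tobacco. SAP 6.1 and Protocol 4.1 speak of quitting any tobacco product, and Protocol 4.1 ties that to the Prochaska result. SAP 7.4.6 also says a person must see the benefit of not smoking before entering Action, which an assigned switch does not show.
4. Must a switcher give that answer? No. Protocol 4.1 calls the whole trial a smoking study, 6.3.6 uses smoking for use of either product, and 6.7.1.1 sends both arms to smoking rooms. But 6.7.1.1 also separates using CHTP 1.2 from smoking CC, and the definition of CHTP 1.2 stresses that its tobacco is not burned. Usage is mixed.

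The figure showing the questionnaire's structure (SAP Figure 3) was not in the text available, so any routing note in it could not be checked.

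**Range of the effect**

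Inputs:

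- N = 80 planned in the CHTP 1.2 arm (SAP 6.1).
- f = share of that arm that has replaced cigarettes. SAP 8 expects at least 50% to remain in the ambulatory per-protocol set, used here as a rough lower figure.
- q = share of those who answer that they quit. The documents do not give it, so it is an assumption shown from 0 to 100%.
- Assumption: nobody in either arm quits all tobacco.

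Formula: subjects in Action through switching = N × f × q. For f = 50% and q = 25%: 80 × 0.50 × 0.25 = 10, or 12.5% of the arm.

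| f | q = 0 | q = 25% | q = 50% | q = 100% |
|---|---|---|---|---|
| 50% | 0 | 10 (12.5%) | 20 (25%) | 40 (50%) |
| 75% | 0 | 15 (18.8%) | 30 (37.5%) | 60 (75%) |
| 100% | 0 | 20 (25%) | 40 (50%) | 80 (100%) |

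The CC arm (about 40) has none by this route in any cell. The value f = 50% is only a proxy: SAP Table 12 lets a compliant subject smoke up to 2 CC on a day and 0.5 CC per day on average, so per-protocol status does not mean that cigarettes have stopped.

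**The case against.** The strongest reply is that the scoring does not place anyone in Action; the subject's answer does. At Visit 4 both arms complete the mCEQ and FTND in the same evening slot (Protocol Table 17). Both use smoking vocabulary, and the FTND is anchored to the assigned product. A CHTP 1.2 user may well carry that reading over, say that he or she smokes, and be staged on intention as intended. The endpoint is also exploratory, objective 3 has no between-arm clause, and no test or claim hangs on it. Table 15.2.5.8.1 will show whether Action clusters among CHTP 1.2 users, and the ITUQ separately records intention to use CHTP 1.2 with or without cigarettes.

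Much of this stands, and it limits the point to an ambiguity of unknown size. It does not remove it. The by-category table can show clustering but cannot separate the tobacco-free from the switched, and no planned table recovers an intention that was not asked.

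A reader might infer three stronger things that the documents do not support:

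- **Switchers' intention to quit may have fallen unseen.** Criterion 7 puts essentially everyone in the lowest stage at screening, so no fall in stage is possible in either arm.
- **The cigarette-free days in confinement move CHTP 1.2 subjects from Contemplation to Preparation through item 2.** The scoring asks for a quit attempt, and allocated substitution is not plainly one. An exclusive switcher would also have to count CHTP 1.2 as smoking in item 1 but not in item 2.
- **The CHTP 1.2 use category consists of people who replaced cigarettes.** It starts at 70% of use (SAP Table 7), so up to 30% may be cigarettes.

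**Conclusion.** The point holds as an undefined reference product with a possible one-arm consequence. Action at Day 90 in the CHTP 1.2 arm may combine subjects who left tobacco with subjects who changed product as assigned, and the planned tables do not separate them. A reader might go further and say that the table by arm must reflect allocation rather than intention. That does not follow, because it depends on how subjects read the item.

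The size runs from nothing (q = 0) to 40 of 80 at f = 50%, and to the whole arm at the extreme. It rests on q, which is undocumented, on f, which is borrowed from per-protocol retention, and on nobody quitting all tobacco. No primary or secondary result is affected. This is a worthwhile, inexpensive improvement to an exploratory, descriptive table.

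**What to change.** In SAP 12.5.3.1.5, keep the scoring algorithm and split the Day 90 Action row of Tables 15.2.5.8 and 15.2.5.8.1, using the product use diary and the definition in SAP 10.7:

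- Action, no tobacco product for at least 14 days;
- Action, still using CHTP 1.2 or other tobacco (intention not asked);
- Action, diary data missing.

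Add a tabulation of item 3 by arm on the FAS (30 days, 6 months, not thinking of quitting, not asked). State that only the first Action row is interpreted as quitting tobacco.

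Do not declare in the SAP that quitting means all tobacco products. That cannot change the question put to subjects and would mislabel their answers.

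The cost is a few lines of SAP text, the extra rows and one small table, all from data already collected. SAP section 3 allows amendments up to database lock. The downside is a slightly larger table and a less favourable Action count in the CHTP 1.2 arm.

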7.4.7 Cough Assessment

Subjects will be asked to self-report and to assess the respiratory symptom “cough” on a VAS, on three Likert scales, and with an open question. Assessment of cough reflecting the cough symptoms in the last 24 hours will be conducted irrespective of the time of product use.

Subjects will be asked if they have experienced a regular need to cough, e.g., whether they have coughed several times in the previous 24 hours prior to assessment. If the answer is “yes”, subjects will be asked to complete a VAS, 3 Likert scale questions and the open question.

On the VAS, subjects will assess how bothersome their cough was during the previous 24 hours. The VAS ranges from “not bothering me at all” to “extremely bothersome”.

Furthermore, subjects will assess the intensity and frequency of cough and the amount of sputum production during the previous 24 hours on Likert scales as presented in **Table 6**.

Table 6 Cough Assessment Likert Scales

Question	Likert Scale
1 The intensity of cough	1 = very mild 2 = mild 3 = moderate 4 = severe 5 = very severe
2 The frequency of cough	1 = rarely 2 = sometimes 3 = fairly often 4 = often 5 = almost always
3 The amount of sputum production	0 = no sputum 1 = a moderate amount of sputum; 2 = a larger amount of sputum; 3 = a very large amount of sputum.

Finally, subjects will be asked to share any other important observations with the site collaborators about their coughing.

Cough Assessment will be done daily from Day -2 to Day 6 prior product use but no later than 11:30 AM. It will also be done at Day 30 Visit, Day 60 Visit, and Day 90 Visit (second day of the respective visits) no later than 11:30 AM, irrespective of product use.

7.5 Categorical Variables

The categorical variables used in this study are shown below (Table 7).

Table 7: Categorical Variables Definitions	
Variable	Categories
Action taken with study product due to adverse event	Product use interrupted Product use withdrawn Product use reduced None
Adverse event expectedness	No Yes
Adverse event relationship to IP	Related Not related
Adverse event relationship to Study Procedures	Related Not related
Adverse event severity	Mild Moderate Severe
Attempt to quit (based on number of days without tobacco use)	30 days ([14-44 days]) 60 days ([44-74 days]) 90 days (>74 days)
BMI (kg/m ²)	Underweight: < 18.5 Normal range: ≥ 18.5 and < 25.0 Overweight: ≥ 25.0 and < 30.0 Obese: ≥ 30.0
CO breath test level (ppm)	≤ 10 > 10
COHb level	≤ 2% > 2%
Daily CC consumption over the last 6 weeks as reported at Admission (per day).	10-19 >19
Detailed Product use Categories for CHTP 1.2 arm	Exclusive CHTP 1.2 ([95-100]%) Predominantly CHTP 1.2 ([70-95]%) Dual Mostly CHTP 1.2 ([60-70]%) Dual Balanced ([40-60]%) Dual Mostly CC ([30-40]%) Predominantly CC ([5-30]%) Exclusive CC ([0-5]%)
FTND total score	Mild: 0 – 3 Moderate: 4 – 6 Severe: 7 – 10

**Table 7: Categorical Variables Definitions**

Variable	Categories
General Product Use Categories for CHTP 1.2 arm	CHTP 1.2 [70-100%] Dual]30-70%[CC [0-30%]
ISO tar yields	1 – 5 mg 6 – 8 mg 8– 10 mg > 10 mg
Nicotine level	<= 0.6 mg > 0.6 to <= 1 mg
Outcome of adverse event	Fatal Not recovered or not resolved Recovered or resolved Recovered or resolved with sequelae Recovering or resolving Unknown
Product Preference	CC CHTP 1.2 No Preference
Product Use Safety Time Periods	Period 1 ([Day 1-(Discharge from confinement)]) Period 2 (]Discharge from confinement – Day 30 Visit]) Period 3 (]Day 30 Visit- Day 60 Visit]) Period 4 (]Day 60 Visit -Day 90 Visit])
Product Use Time Periods	Period 1 ([Day 1-Discharge from confinement]) Period 2 ([Discharge from confinement – Day 30 Visit]) Period 3 (]Day 30 Visit- Day 60 Visit]) Period 4 (]Day 60 Visit- Day 90 Visit])
Safety Time Periods	Product Test ([Product trial – Randomization]) Randomized period: 
 • Confinement ([Day 1-Discharge from Confinement]) • Ambulatory (]Discharge from Confinement-Discharge from Ambulatory]) • Safety Follow-up (]Discharge from Ambulatory – End of Study])
Seriousness Criteria	Fatal Life-threatening Requires hospitalization

**Table 7: Categorical Variables Definitions**

Variable	Categories
	Results in disability/incapacity
	Congenital anomaly/birth defect
	Other medically important event

8 SAMPLE SIZE JUSTIFICATION

The following discussion addresses the ability to detect a reduction of 50% or more in the levels of MHBMA, 3-HPMA, S-PMA, and COHb on Day 5 and in total NNAL after 90 days in smokers switching from CC to the CHTP 1.2 as compared to smokers continuing to use CC, using a one-sided test with 2.5% type I error probability.

Table 8 describes the expected coefficients of variation (CV) and mean ratios (MR) between CHTP 1.2 and the one control arm based on data from a controlled, randomized, open-label, 3-arm parallel single-center confinement study that investigated exposure to selected smoke constituents in smokers switching from CC to smoking article cigarettes for 5 days, the YVD-CS01-EU study (ClinicalTrials.gov ID: NCT00812279) sponsored by PMI (Lüdicke et al, 2016).

Table 8 Expected Mean Ratios and Coefficients of Variation for CHTP 1.2/CC after 5 Days of exposure

	CHTP 1.2/CC MR (CV)
COHb	0.40 (0.32)
3-HPMA	0.30 (0.50)
MHBMA	0.15 (0.70)
S-PMA	0.20 (0.70)

Abbreviations: 3-HPMA = 3-hydroxypropylmercapturic acid; CC = Combustible cigarettes; COHb = Carboxyhemoglobin; CV = Coefficients of variation; MHBMA = Monohydroxybutenyl mercapyuric acid; MR = Mean ratios; S-PMA = S-phenylmercapturic acid; CHTP 1.2 = Carbon Heated Tobacco Product 1.2.

Table 9 describes the expected coefficients of variation (CV) and mean ratios (MR) in total NNAL after 90 days between CHTP 1.2 and the one control arm based on a randomized, controlled, forced-switching, open-label, parallel-group, single-center study in 90 male and female adult smokers to evaluate six biomarkers of tobacco smoke exposure over a 12-week period of unrestricted smoking in the participants' normal life setting (Frost et al, 2008).

**Table 9 Expected Mean Ratios and Coefficients of Variation for CHTP 1.2/CC after 90 Days of exposure**

	CHTP 1.2/CC MR (CV)
Total NNAL	0.30 (0.60)

Abbreviations: Total NNAL = Total 4-(methylnitrosamino)-1-(3-pyridyl)-1-butanol; MR = Mean ratio; CHTP 1.2 = Carbon Heated Tobacco Product 1.2; CC = Combustible cigarettes; CV = Coefficient of variation.

The power to detect a reduction was computed and is presented below.

Table 10 describes the expected power to detect a reduction of 50% or more in the levels of MHBMA, 3-HPMA, S-PMA, and COHb in CHTP 1.2 arm compared to the CC arm after 5 days of exposure and total NNAL after 90 days of exposure, with a one sided test with 2.5% type I error probability using the assumptions from YVD-CS01-EU and, and 120 randomized subjects in a 2:1 ratio (80 in CHTP 1.2 arm and 40 in CC arm). It is assumed that a minimal number of subjects will be excluded from the PP set in confinement for both arms and CC in ambulatory, whereas at least 50% will remain in the PP set in ambulatory for CHTP 1.2, therefore a 2:1 randomization ratio was chosen.

Table 10 Expected Power

Assumptions	Reduction					
	50%	51%	52%	53%	54%	55%
YVD-CS01-EU	94%	88%	81%	70%	56%	38%

The test-wise powers to detect a reduction of 50% or more in the levels of MHBMA, 3-HPMA, S-PMA, and COHb on Day 5 and in total NNAL after 90 days in smokers switching from CC to the CHTP 1.2 as compared to smokers continuing to use CC, using a one-sided test with 2.5% type I error probability using the assumptions from YVD-CS01-EU, and 120 randomized subjects in a 2:1 ratio (80 in CHTP 1.2 arm and 40 in CC arm) are described in **Table 11**.

Table 11 Test-Wise Power

Parameter	Test-Wise Power
COHb	96%
3-HPMA	>99%
MHBMA	>99%
S-PMA	>99%

Total NNAL 98%

Given the above calculation, the sample size was considered sufficient to have more than 80% power to detect a reduction of 50% or more in the levels of MHBMA, 3-HPMA, S-PMA, and COHb in CHTP 1.2 arm compared to the CC arm after 5 days of exposure, and in the levels of total NNAL in the CHTP 1.2 arm compared to the CC arm after 90 days of exposure, using a one sided test with 2.5% type I error probability.

